				Additional information about test procedures: Intra-procedure stopping criteria:

Procedure name(s)	Tier	Eligibility	Exclusion criteria	Additional information about test procedures and permissible clinical variation
				Stop if participant cannot tolerate the procedure, requests that the test be terminated, or becomes vasovagal.
Skin biopsy	3	All participants are eligible for this test through random assignment. Participants with relevant symptoms (as outlined in the applicable SOP) will be oversampled for assignment as follows: ANY of the following: Neurologic exam for neuropathy Orthostatic hypotension Postural orthostatic tachycardia Symptoms of dysautonomia Feeling faint, dizzy, or goofy or difficulty thinking soon after standing	 Taking blood thinning medication unless prescribing provider confirms they can be held for 7 days prior to and 1 day post procedure. These medications include: Direct oral anticoagulants (e.g. rivaroxaban, dabigatran, apixaban or edoxaban) Vitamin K antagonists (e.g. warfarin) Low molecular weight heparins (e.g. bemiparin, certoparin, dalteparin, enoxaparin, nadroparin, parnaparin, reviparin or tinzaparin) Heparin Anti-platelet agents (e.g. clopidogrel, ticagrelor, or prasugrel) Aspirin ≤ 325 mg daily (Aspirin ≤ 325mg may be included without medication hold) Intrinsic bleeding disorder (liver failure, uremia, other known bleeding disorder, history of excessive bleeding during procedures), including those with the following 	Permissible clinical variation: Side of biopsy should be selected based on presence of symptoms or, if none, the non-dominant side Additional information about test procedures: Three biopsies are obtained: one each from the posterior cervical, distal leg and distal thigh regions Each of the three biopsies taken should be approximately 3 mm

Procedure name(s)	Tier	Eligibility	Exclusion criteria	Additional information about test procedures and permissible clinical variation
			abnormalities (use most recent result within the prior year): INR > 1.3 times upper limit of normal PT > 13 seconds Platelets < 125,000 /mL Contraindication or known allergy to lidocaine Patients who have a history of poor wound healing or who are prone to keloid formation Pregnant or < 3 months post-partum.	

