Muscle biopsy	3	Only infected participants who meet the eligibility criteria as follows may be asked to complete this assessment: ANY of the following: • Moderate to severe muscle weakness or pain • Moderate to severe post-exertional malaise Participants who also qualify for CPET will be offered the option to do a pre-CPET muscle biopsy and a post-CPET muscle biopsy at the same site	Taking blood thinning medication unless prescribing provider confirms they can be held for 7 days prior to and 1 day post procedure, including Direct oral anticoagulants (e.g. rivaroxaban, dabigatran, apixaban or edoxaban) Vitamin K antagonists (e.g. warfarin) Low molecular weight heparins (e.g. bemiparin, certoparin, dalteparin, enoxaparin, nadroparin, parnaparin, reviparin or tinzaparin) Heparin Anti-platelet agents (e.g. clopidogrel, ticagrelor or prasugrel) Aspirin	 Side of biopsy is at clinician discretion A 5 or 6 mm Bergstrom-style biopsy needle is permissible depending on local equipment availability Additional information about test procedures: Participants must fast for 4 hours prior to procedure (medications with sips of water are acceptable) One biopsy is obtained from the vastus lateralis; multiple passes at same biopsy site are permissible to obtain weight of at least 150 mg (approximately a 5 mm biopsy) If participant agrees to pre/post-CPET biopsy, a second biopsy

[figure not shown]
Procedure name(s)	Tier	Eligibility	Exclusion criteria	Additional information about test procedures and permissible clinical variation
			 Non-steroidal anti-inflammatory medications (e.g. ibuprofen, ketorolac, naproxen, diclofenac, indomethacin, celecoxib, meloxicam) Intrinsic bleeding disorder (liver failure, uremia, other known bleeding disorder, history of excessive bleeding during procedures), including those with the following abnormalities (use most recent result within the prior year): INR > 1.3 times upper limit of normal PT > 13 seconds aPPT > 36 seconds Platelets < 125,000/mL Contraindication or known allergy to lidocaine Patients who have a history of poor wound healing or who are prone to keloid formation Pregnant or < 3 months post-partum. 	sample is obtained from the same leg and same muscle post-CPET

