Lumbar puncture with or without imaging (fluoroscopy or ultrasound guidance)	3	Only infected participants are eligible for this test through random assignment. Participants with relevant symptoms (as outlined in the applicable SOP) will be oversampled for assignment as follows: ANY of the following: Headaches Leptomeningeal, dural, or parenchymal enhancement	 Participants opting out of the CSF biospecimen collection for central processing Any intracranial space-occupying lesion with mass effect, posterior fossa mass or cerebral herniation as determined by clinical examination (e.g., papilledema, depressed 	 Use of fluoroscopy or ultrasound guidance is at discretion of site clinician and should consider patient factors. Choice of positioning (left or right lateral, or upright) and intercostal space (L3-4 or L4-5) is at

Procedure name(s) Tier	Eligibility	Exclusion criteria	Additional information about test procedures and permissible clinical variation
	Abnormal NIH Toolbox or other cognitive test score	mental status, focal neurologic findings), brain MRI or head CT • Taking blood thinning medication, unless prescribing provider confirms they can be held for 7 days prior to and 1 day post procedure. These medications include: ○ Direct oral anticoagulants (e.g. rivaroxaban, dabigatran, apixaban or edoxaban) ○ Vitamin K antagonists (e.g. warfarin) ○ Low molecular weight heparins (e.g. bemiparin, certoparin, dalteparin, enoxaparin, nadroparin, parnaparin, reviparin or tinzaparin) ○ Heparin ○ Anti-platelet agents (e.g. clopidogrel, ticagrelor or prasugrel) ○ Aspirin > 81 mg (Aspirin ≤ 81 mg may be included without medication hold) • Intrinsic bleeding disorder (liver failure, uremia, other known bleeding disorder, history of excessive bleeding during procedures), including those with the following abnormalities (use most recent result within the prior 30 days):	discretion of site clinician and should consider patient factors. Additional information about test procedures: Sedation or anesthesia is not permitted Up to three attempts are permissible. Intra-procedure stopping criteria: Stop procedure if participant experiences lower extremity neurologic symptoms.

Procedure name(s)	Tier	Eligibility	Exclusion criteria	Additional information about test procedures and permissible clinical variation

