			 Creatinine > 2 mg/dL ECG with unstable ischemic disease Taking blood thinning medication, unless prescribing provider confirms they can be held for 7 days prior to and 1 day post procedure. These medications include: Direct oral anticoagulants (e.g. rivaroxaban, dabigatran, apixaban or edoxaban) Vitamin K antagonists (e.g. warfarin) Low molecular weight heparins (e.g. bemiparin, certoparin, dalteparin, enoxaparin, nadroparin, parnaparin, reviparin or tinzaparin) Heparin Anti-platelet agents (e.g. clopidogrel, ticagrelor, prasugrel) Aspirin > 81 mg daily (Aspirin ≤ 81 mg may be included without medication hold) Active cardiac ischemia or unstable angina FVC < 50% or FEV1 < 50% BMI > 50 kg/m² 	 A total of 4 bronchial brushings are collected from either the left or right lower lobe A Supraglottic Sample Is Taken A post-procedure chest X ray is required Intra-procedure stopping criteria: Bronchoscopy will be stopped if the following abnormalities are detected for longer than one minute: Systolic blood pressure 90 or > 160 mmHg, Respiratory rate > 25 breaths or < 8 breaths per minute Persistent heart rate < 60 or > 120 beats per minute Irregular heart rhythm EtCO2 > 50 mmHg or an absent ETCO2 waveform and/or oxygen saturation (SaO2) below 90% despite oxygen supplementation If a participant is uncomfortable or agitated during the procedure despite safe maximal doses of procedural sedation, the procedure can be aborted by the operating physician Additionally, the procedure can be stopped at any point at the discretion of the investigator performing the bronchoscopy.

Procedure name(s)	Tier	Eligibility	Exclusion criteria	Additional information about test procedures and permissible clinical variation
			 Hospitalization within 6 weeks of procedure Non-elective intubation within last 6 months Active upper respiratory infection within 2 weeks of procedure Active tuberculosis Contraindication to sedation Allergy to lidocaine Pregnant or < 3 months postpartum. 	Hospitalization criteria: Significant cough persisting beyond 2 hours after completion of procedure Persistent hypoxia <90% at end of monitoring time Persistent tachycardia >130 bpm at end of monitoring time Hemodynamically unstable arrhythmia Unexpected altered mental status during or after procedure Significant hemoptysis >50 ml Requirement for bronchodilator every 2 hours on more than 3 occasions Pneumothorax

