		performing RECOVER invasive cardiopulmonary exercise testing	rivaroxaban, dabigatran, apixaban or edoxaban) Vitamin K antagonists (e.g., warfarin) Low molecular weight heparins (e.g., bemiparin, certoparin, dalteparin, enoxaparin, nadroparin, parnaparin, reviparin or tinzaparin) Heparin Anti-platelet agents (e.g., clopidogrel, ticagrelor, prasugrel) Aspirin > 325 mg daily (Aspirin < 325 mg may be included without medication hold) Intrinsic bleeding disorder (liver failure, uremia, other known bleeding disorder, history of excessive bleeding during procedures) Any of the following labs with abnormalities within 21 days of procedure: INR > 1.3 times upper limit of normal PT > 13 seconds aPPT > 36 seconds Platelets < 150,000/mL Hemoglobin < 11 g/dL BUN > 60 mg/dL Creatinine > 2 mg/dL	 If procedural sedation is selected, personnel administering sedation, choice of sedation agents, dosage limits and intervals, and credentialing must be managed according to local institutional policy, but may not exceed limits indicated in the SOP. Monitoring during and post-procedure must be conducted in accordance with local institutional policy. Additional information about test procedures Participant must fast for 6 hours prior to procedure Results of screening labs are determined to be abnormal through both the local reference ranges and clinician discretion Intra-procedure stopping criteria: ECG signifying current myocardial injury or potentially lethal arrhythmias Systemic hypotension (e.g., mean arterial blood pressure <50 mmHg) Extreme hypertension (e.g., mean arterial pressure > 110 mmHg) Syncope or pre-syncope or lightheadedness Peripheral oxyhemoglobin saturation level <80%

Procedure name(s)	Tier	Eligibility	Exclusion criteria	Additional information about test procedures and permissible clinical variation

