			parnaparin, reviparin or tinzaparin) Heparin Anti-platelet agents (e.g. clopidogrel, ticagrelor, prasugrel) Non-steroidal anti-inflammatory medications (e.g. ibuprofen, ketorolac, naproxen, diclofenac, indomethacin, celecoxib, meloxicam) Aspirin > 81 mg (aspirin < 81 mg may be included without medication hold) Other aspirincontaining medications (e.g. Alka Seltzer, Excedrin) Iron supplements Intrinsic bleeding disorder (liver failure, uremia, other known bleeding disorder, history of excessive bleeding during procedures), including those with the following abnormalities (use most recent result within the prior year): Hemoglobin < 10 g/dL INR > 1.3 PT>13 seconds PT>13 seconds Platelets < 125,000 /mL	 Participants must alter food and liquid intake pre-procedure according to bowel preparation instructions; medications may be taken 2 hours or more before procedure Colonoscopy involves 6 total biopsies (1 double bite) from each of three locations: terminal ileum, proximal ascending colon and descending colon Upper endoscopy involves 4 biopsies (1 double bite) from each of two locations: the stomach and duodenum Intra-procedure stopping criteria: Significant hemodynamic changes such as significant decrease in heart rate, hypotension, hypoxia, or tear in the intestines At the discretion of endoscopist or anesthesiologist

Procedure name(s)	Tier	Eligibility	Exclusion criteria	Additional information about test procedures and permissible clinical variation
			Severe immunosuppressive medications including:	

Table 9 Medications that should be stopped (if possible) prior to Autonomic Test Suite

[figure not shown]
Medication	Days to stop	Medication	Days to stop	Medication	Days to stop	Medication	Days to stop
Α		D		Lofexidine (Lucemyra)	3	Scopolamine	3
Abilify (Aripiprazole)	7	Darbid	7	Lomotil	3	Sectral	1
Acebutolol	1	Darifenacin (Enablex)	4	Lonamin	4	Serevent (Salmeterol)	2
Aclidinium (Tudorza Pressair)	1	Desipramine	7	М		Seroquel	2
Acyclovir	5	Desloratadine(Clarin ex)	6	Marezine	4	Sertraline	5
Adalat	1	Desoxyn	3	Maxair (Pirabuterol)	1	Serzone	7
Adderall	3	Desvenlafaxine (Pristiq)	3	Meclizine	2	Silodosin (Rapaflo)	5
Adipex	4	Desyrel	7	Mepenzolate	2	Sinequan	5
Akineton	4	Detrol	2	Mestinon	1	Solifenacin (Vesicare)	7
Akovaz (Ephedrine)	1	Dexmethylphenidate (Focalin)	1	Metaproterenol	2	Solabegron	1
Albuterol	1	Dexchlorpheniramine	4	Methyldopa	1	Solrimaferol (Sunosi)	2
Aldomet	1	Dicyclomine	2	Methylphenidate	3	Spiriva (Tiotropium)	7

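### Appendix 5, skin biopsy: as printed, the aspirin line requires a hold for, and exempts from a hold, the same doses (325 mg daily or less); the first sign should probably be >

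*Protocol*

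**What the plan says.** The skin biopsy row of Protocol Section 19.5 (Appendix 5) opens its exclusions with "Taking blood thinning medication unless prescribing provider confirms they can be held for 7 days prior to and 1 day post procedure", followed by a list of drugs that is introduced as inclusive rather than exhaustive. The last item is "Aspirin ≤ 325 mg daily (Aspirin ≤ 325mg may be included without medication hold".

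Section 19.4 (Appendix 4) marks skin biopsy as greater than minimal risk. Appendix 5 opens it to all participants by random assignment, with oversampling on relevant symptoms, and specifies three biopsies. Section 4.1 names bleeding among the risks of biopsy. Section 6.1 requires a licensed physician to confirm, for every Tier 3 test above minimal risk, that no listed exclusion applies. It adds that the criteria also appear as checklists in each procedure's SOP.

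**The concern.** A drug on this list excludes the participant unless the prescriber agrees to a hold. Aspirin at 325 mg daily or less is on the list, so the list item asks for a hold or an exclusion. The parenthesis on the same line admits the same doses with no hold. Both instructions cannot apply to one participant. The range that a reader would expect to see listed, above 325 mg, is not named.

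At stake is the consistent application of a bleeding-safety criterion. For a participant on low-dose aspirin, one site could require a hold and another proceed without one, each citing the same line. Section 14.3 treats any noncompliance with the protocol as a deviation, so the same biopsy could be recorded as compliant or not, depending on which half of the line is followed.

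**Working it through.** No sample size, power or error-rate figure is involved. The check compares the two dose sets on each aspirin line in Appendix 5, with doses in mg.

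| Row | Aspirin text | Needs hold | Exempt | Overlap |
|---|---|---|---|---|
| Skin biopsy | "Aspirin ≤ 325 mg daily (Aspirin ≤ 325mg may be included without medication hold" | 325 or less | 325 or less | complete |
| Muscle biopsy | "Anti-platelet agents (e.g. clopidogrel, ticagrelor or prasugrel) Aspirin" | any dose | none stated | none |
| Lumbar puncture | "Aspirin > 81 mg (Aspirin ≤ 81 mg may be included without medication hold" | above 81 | 81 or less | none |
| Flexible bronchoscopy | "Aspirin > 81 mg daily (Aspirin ≤ 81 mg may be included without medication hold" | above 81 | 81 or less | none |
| Right heart catheterization | "Aspirin > 325 mg daily (Aspirin < 325 mg may be included without medication hold" | above 325 | below 325 | none |
| Colonoscopy | "Aspirin > 81 mg (aspirin < 81 mg may be included without medication hold" | above 81 | below 81 | none |

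1. Six rows list aspirin. Muscle biopsy prints no dose, which leaves 6 − 1 = 5 dose-specific lines.
2. The two ranges overlap in 1 of those 5 lines, and there the overlap is the whole range.
3. The other four lines all put > in the first position. Right heart catheterization does so at 325 mg, so the closest parallel to the skin biopsy line carries the opposite sign.
4. With > in the first position, the skin biopsy line would list doses above 325 mg and exempt doses of 325 mg or less. Every dose would then fall in exactly one set, as in the lumbar puncture and bronchoscopy lines. (The right heart catheterization and colonoscopy lines leave the threshold dose itself unassigned, so they are not the form to copy.)
5. Could the sign be a reading fault? The skin biopsy row has six comparison signs: the two ≤ on the aspirin line, two > and two <. Three of the other four stand in "INR > 1.3 times upper limit of normal PT > 13 seconds Platelets < 125,000 /mL", and the fourth is the limit of less than 3 months post-partum. All four make clinical sense. The > and ≤ signs are also printed distinctly in the lumbar puncture and bronchoscopy lines. Against that, the bronchoscopy stopping criteria show a systolic limit of 90 with no sign before it, so signs in this appendix have not all survived reading.

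**The case against.** The strongest reply is that the fault may not be in the protocol at all. The text is machine-read and visibly damaged in places: garbled words in Section 3.1, a phrase repeated mid-sentence in the oral glucose tolerance entry of Table 1, and the missing sign in the bronchoscopy row. A sign repeated from a few words later on the same line would be a similar fault, and four sound signs nearby do not rule out one bad one. This stands. It limits the point to the text as supplied and makes checking the source PDF the first step.

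The second reply is that the row still works. The parenthesis expressly permits doses of 325 mg or less, and the general opening words cover higher doses because the list is not exhaustive. Someone who followed the list item alone would err towards caution, asking for a hold with the prescriber's agreement or excluding the participant. This also stands, and it is why the point is minor.

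The third reply is that physician review and the SOP checklist provide protection. It stands in part. The SOP is not among the documents and may already be right. But Section 6.1.2 requires SOPs to be consistent with the approved protocol, so a correct checklist would not remove the need to correct the protocol line.

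A reader might infer that the line lets participants on high-dose aspirin be biopsied without a hold, or that sites have been applying a wrong rule. The documents support neither: the opening words still reach doses above 325 mg, and no instruction to sites other than this row can be seen.

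**Conclusion.** As supplied, the line contradicts itself, and the parallel rows show that the intended range is above 325 mg daily. This is a minor wording error in an operative safety criterion. No design choice is in dispute.

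Its size is one sign on one of five dose-specific aspirin lines. The documents do not say how many participants take aspirin, so the number affected is unknown. It would be wrong to infer any consequence for the comparison of infected and uninfected participants, or for the skin biopsy results: no estimand, sample size or analysis depends on this line.

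The conclusion assumes that the sign was read correctly from the PDF. If the PDF prints >, there is no error.

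**What to change.** Check the sign in the source PDF. If it prints ≤, change the first sign on the skin biopsy aspirin line to >, so that the item lists doses above 325 mg daily, and leave the parenthesis exempting 325 mg or less as it is. Confirm that the skin biopsy SOP checklist states the same rule. If the PDF already prints >, no change is needed.

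The cost is one sign in one table row and one checklist comparison, carried in the next IRB amendment. Sample size, schedule and analysis are unaffected.

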Site staff are ultimately responsible for ensuring participants do not meet safety exclusion criteria after they have been selected for a test, as not all exclusion criteria are available in REDCap. Pre-test assessments that are conducted once participant is assigned to a test to determine safety exclusion criteria must then be documented in REDCap. SOPs for these tests make clear that ineligible participants might be assigned tests because not all exclusion information is known to REDCap. These safety exclusion criteria are also

available as checklists for site staff in the respective SOP. For all Tier 3 tests that are more than minimal risk, a licensed physician will review the exclusion criteria for that test and confirm that the subject does not meet any of the specified safety exclusion criteria.

Procedures in Tier 3 will only be performed concurrently when clinically appropriate. Complete information regarding how tests will be assigned will be in each assessment's SOP. Tier 2 and 3 procedure eligibility, exclusion criteria, and clinical variance affecting the risk/benefit assessment are found in **Appendix 5**: Tier 2 and 3 eligibility, exclusion criteria.

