			 INR > 1.4 times upper limit of normal Platelets < 100,000/mL Skin infection at the planned puncture site Allergy to lidocaine, iodine (may use chlorhexidine as an alternative), or latex (may use latex free gloves as an alternative) Pregnant or < 3 months post-partum 	
Facility-based polysomnography	3	All participants are eligible for this test through random assignment. Participants with relevant symptoms (as outlined in the applicable SOP) will be oversampled for assignment as follows: ANY of the following: Qualifies for home polysomnography and uses home oxygen or CPAP Central sleep apnea Moderate sleep disturbance Acting out dreams Restless legs Moderate to severe insomnia Decreased oxygen for extended sleep duration without sleep apnea	Pregnant or < 3 months post- partum (excluded for data quality, not for safety)	Permissible clinical variation, depending on local equipment availability and patient factors: Sites may use 3 or 6 EEG sites Submental electromyography may be measured by 1-3 chin EMGs ECG may use 2 or 3-lead precordial placement Airflow may be measured via nasal pressure flow, PAP flow or oronasal thermocouple Snoring vibration may or may not be measured Leg movements may be measured by 1-2 EMG signals per leg Minimum and desired sampling rates (Hz) are provided in the SOP
Autonomic testing: Heart rate variability	3	All participants are eligible for this test through random assignment. Participants with relevant symptoms (as outlined in the applicable SOP) will be oversampled for assignment as follows:	 Pregnant or < 3 months post- partum Known clinically severe left ventricular outflow obstruction, critical mitral stenosis, or 	Additional Information: Certain medications interfere with the results. Participants are advised that optimal results will be

Procedure name(s)	Tier	Eligibility	Exclusion criteria	Additional information about test procedures and permissible clinical variation

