			 Neuromuscular impairment that precludes incremental exercise on the ergometer being used to conduct the study Pregnant or < 3 months post- partum 	 Severe oxygen desaturation, SpO2<80% when accompanied by signs of severe hypoxia within 2 minutes of unloaded pedaling Neurologic compromise such as mental confusion or loss of coordination Inability to coordinate a regular cadence of >40 cycles/minute
Invasive cardiopulmonary exercise testing	3	Only infected participants who meet the eligibility criteria as follows may be asked to complete this assessment: ALL of the following: Shortness of breath Non-reduced ejection fraction	All exclusions for CPET and right heart catheterization apply, plus: Inability to exercise on cycle ergometer (treadmill is not permitted for iCPET) Allergy to lidocaine	 Additional information about test procedures: All additional information for CPET and right heart catheterization applies, plus: Participants should fast for at least two hours prior to procedure Procedure site may involve right or left internal jugular or brachial vein only, not femoral vein. In addition, a right or left radial arterial catheter is placed Side of placement is at discretion of the local clinician and should take into account patient factors Intra-procedure stopping criteria All intra-procedure stopping criteria for CPET and right heart catheterization apply, plus: Markedly abnormal resting supine hemodynamic values (i.e. PVT > 10 WU, PCWP > 40 mgHg)

Procedure name(s)	Tier	Eligibility	Exclusion criteria	Additional information about test procedures and permissible clinical variation

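### All six platelet exclusion limits in Appendix 5 are printed per mL, so read literally the numeric limit excludes no one at any plausible count

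*Protocol*

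**What the plan says.** Appendix 5 of the protocol (Section 19.5) lists exclusion criteria by procedure. Six rows contain a platelet limit:

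- Skin biopsy: "Platelets < 125,000 /mL". Colonoscopy prints the same figure and unit.
- Muscle biopsy: "Platelets < 125,000/mL".
- Lumbar puncture: "Platelets < 100,000/mL". Flexible bronchoscopy prints the same figure and unit.
- Right heart catheterization: "Platelets < 150,000/mL".

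Invasive CPET has no platelet figure of its own. Its row says "All exclusions for CPET and right heart catheterization apply, plus" and then adds further items, so it takes over the catheterization limit.

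In five of the six rows the platelet figure is one of several laboratory abnormalities listed under intrinsic bleeding disorder. In the catheterization row the bleeding disorder is a separate item, and the platelet figure stands in a list of abnormal laboratory results. For that procedure the protocol adds: "Results of screening labs are determined to be abnormal through both the local reference ranges and clinician discretion". The invasive CPET row carries over the additional information given for catheterization.

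For every Tier 3 test that is more than minimal risk, Section 6.1 states that "a licensed physician will review the exclusion criteria for that test" and confirms that none of them is met.

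**The concern.** A platelet limit in a safety screen is a decision rule: a participant below it does not undergo the procedure. The unit sets the scale of that rule, and per mL puts these limits a thousandfold below the same numerals per microlitre. The unit is the same in all six rows and no other part of the protocol states a platelet count in another unit, so a reader cannot settle the intended scale from the document. Other limits in the catheterization list, such as hemoglobin in g/dL and creatinine in mg/dL, are on scales that can exclude someone.

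All seven procedures are marked in Appendix 4 as greater than minimal risk, and Section 4.1 names bleeding among the risks of each. For lumbar puncture it describes bleeding that compresses the spinal cord and needs surgery. Skin biopsy, bronchoscopy and colonoscopy are open to all participants by random assignment, and lumbar puncture to infected participants in the same way. The screen therefore also covers people without relevant symptoms. If the printed figure cannot be used as it stands, each site has to decide for itself which figure to apply.

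**Working it through.** No sample size, power or error rate is involved. The check is a count of the limits, a unit conversion and a comparison.

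**Inputs from the protocol (Appendix 5).** Six printed limits: 125,000 per mL (skin biopsy, muscle biopsy, colonoscopy), 100,000 per mL (lumbar puncture, bronchoscopy) and 150,000 per mL (right heart catheterization, inherited by invasive CPET).

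**Assumption.** The protocol gives no platelet reference range. I take 5,000 to 149,000 per microlitre as a wide range of low counts.

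**Step 1: convert the limits.** 1 mL = 1,000 microlitres (µL), so limit per µL = limit per mL ÷ 1,000.

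- 100,000 ÷ 1,000 = 100 per µL
- 125,000 ÷ 1,000 = 125 per µL
- 150,000 ÷ 1,000 = 150 per µL

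**Step 2: convert the assumed counts.** Count per mL = count per µL × 1,000. The range becomes 5,000,000 to 149,000,000 per mL.

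**Step 3: compare.** A participant is excluded by the number only if count ÷ limit is below 1.

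| Procedure | Printed limit (per mL) | Same limit (per µL) | 5,000,000 ÷ limit | 149,000,000 ÷ limit |
|---|---|---|---|---|
| Skin biopsy | 125,000 | 125 | 40 | 1,192 |
| Muscle biopsy | 125,000 | 125 | 40 | 1,192 |
| Lumbar puncture | 100,000 | 100 | 50 | 1,490 |
| Flexible bronchoscopy | 100,000 | 100 | 50 | 1,490 |
| Right heart catheterization | 150,000 | 150 | 33.3 | 993.3 |
| Colonoscopy | 125,000 | 125 | 40 | 1,192 |

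No ratio comes near 1. The smallest is 33.3, at the lowest assumed count and the highest limit, so the result does not depend on where in the assumed range a participant lies.

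**Step 4: show how much hangs on the unit.** This illustrates sensitivity only and does not say which unit was meant. If the same numerals were read per µL, they would equal 100,000,000 to 150,000,000 per mL, exactly 1,000 times the printed limits. On that reading counts of 5,000 to 50,000 per µL fall below all six limits. A count of 100,000 per µL falls below four (the three at 125,000 and the one at 150,000), and 149,000 per µL falls below the catheterization limit only. On the printed reading none of these counts falls below any limit.

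**The case against.** Four arguments can be made on the other side.

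**The unit may be a reading error.** The text available was read from a PDF, and the point turns on one letter: a micro sign turned into an m would produce exactly this, in all six rows at once. Greek letters survive in the reference list, but no micro sign appears anywhere in the text to show that this symbol survives. This stands as a caution. It is not shown to have happened, and a look at the PDF settles it.

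**No other passage contradicts the limits.** That is true. The protocol gives no reference range, so the judgement that the limits are too low to work rests on an exact conversion and an assumed range of counts. That assumption has to be stated, but the smallest ratio of 33 leaves ample room for a different range.

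**Other safeguards exist.** A reader might infer that a participant with marked thrombocytopenia passes the whole screen. The protocol does not support that. Known bleeding disorders and a history of excessive procedural bleeding are grounds for exclusion without any number. Catheterization results are also judged by local reference ranges and clinician discretion, and this carries over to invasive CPET. A physician reviews the criteria before each of these tests and may well not take the printed unit at face value. All this stands and reduces the practical effect. It does not repair the printed number: the physician's review in Section 6.1 is against the specified criteria, and the clause on local ranges appears in the catheterization row only.

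**Spread is not documented.** A reader might also infer that the same unit already sits in the SOP checklists and in REDCap, or that sites have screened inconsistently. Section 6.1 says that the criteria are available as SOP checklists and that REDCap applies some safety exclusions, but also that REDCap does not hold all of them. Neither the checklists nor the REDCap rules are in the protocol, and nothing says whether the platelet limit is coded or in which unit. Spread is a reason to check and no more than that.

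**Conclusion.** The point holds for the numeric limit itself. Six of six platelet limits are printed per mL, and a seventh procedure inherits one of them. Taken literally they equal 100 to 150 platelets per microlitre and would exclude no one with a count between 5,000 and 149,000 per microlitre. The gap between the per-mL and per-microlitre readings is a factor of 1,000.

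This rests on two assumptions: that the PDF prints the unit as the available text shows it, and that real counts lie in or above the assumed range. The conversion itself is exact.

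The conclusion does not extend to the screen as a whole. The remaining safeguards make the practical effect smaller than the literal one, by an amount the protocol does not allow one to estimate. No harm to any participant is shown, and no estimate, comparison or sample size in the protocol depends on the unit. It remains a safety threshold for procedures of more than minimal risk that cannot do its work as printed, and it should be corrected.

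**What to change.** The sponsor should check the unit in the six Appendix 5 rows against the source PDF, confirm the intended figure and unit for each procedure, and restate the unit in all six rows. The invasive CPET row then follows by reference and needs no separate figure. The SOP checklists, and any REDCap logic that uses a platelet limit, should be checked for the same unit and aligned if affected. No threshold is proposed here; the figure for each procedure is for the sponsor to confirm.

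The cost is a correction to the unit in six table rows, a check of the related SOP checklists and REDCap rules, and the protocol amendment that carries the correction. It needs no additional participants, tests or visits.
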